#### **4.4.4.2 Duration of a Subject in the Trial**

The duration of a subject in the study will be computed as follows:

maximum (date of visit, date of termination form) - date of Visit 1 + 1.

#### **4.4.4.3 Duration of the Study**

The duration of the study will be computed as follows:

maximum of all subjects (date of visit, date of termination form) - minimum for all subjects (date of Visit 1) + 1.

## **5 Statistical Methods and Determination of Sample Size**

The statistical analyses will be performed under the responsibility of the Sponsor's Biostatistics platform using SAS® Version 9.2 software or later.

The results of the statistical analysis will be available in the final CSR.

For descriptive purposes, the statistics in [Table 5.1](#) will be presented.

**Table 5.1: Descriptive Statistics Produced**

Baseline characteristics and follow-up description	Categorical data	Number of subjects Percentage of subjects
	Continuous data	Mean, standard deviation (SD), quartiles, minimum, and maximum
Clinical safety results	Categorical data	Solicited: Number and percentage (95% confidence intervals [CIs]) of subjects Unsolicited: Number and percentage (95% CIs) of subjects, and number of events
Immunogenicity results	Categorical data (seroprotection, seroconversion, cutoff)	Number and percentage (95% CIs) of subjects
	Continuous data (titer / data)	$\text{Log}_{10}$ : Mean and SD Anti- $\text{Log}_{10}$ (work on $\text{Log}_{10}$ distribution, and anti- $\text{Log}_{10}$ applied): Geometric mean, 95% CI of the geometric mean, quartiles, minimum, and maximum. Graphical representation by reverse cumulative distribution curves (RCDCs)

The confidence interval (CI) for the single proportion will be calculated using the exact binomial method (Clopper-Pearson method, quoted by Newcombe [1]; i.e., using the inverse of the beta integral with SAS®).

For immunogenicity results, assuming that  $\text{Log}_{10}$  transformation of the titers/data follows a normal distribution, at first, the mean and the 95% CI will be calculated on  $\text{Log}_{10}$  (titers/data) using the usual calculation for normal distribution (using Student's t distribution with n-1 degree of freedom), then antilog transformations will be applied to the results of calculations, in order to provide geometric means (GMs) and their 95% CI.

## 5.1 Statistical Methods

Summaries of the recruitment and baseline demographic characteristics of the study subjects will be presented. The number of subjects enrolled and their age at enrollment (mean [with standard deviation (SD)], quartiles, minimum and maximum), sex, race, and ethnic origin will be summarized, along with the number and description of protocol deviations.

### 5.1.1 Hypotheses and Statistical Methods for Primary Objectives

There are no primary objectives for this study.

### 5.1.2 Hypotheses and Statistical Methods for Secondary Objectives

There are no secondary objectives for this study.

### 5.1.3 Statistical Methods for Observational Objectives

For the main safety and immunogenicity parameters, 95% CIs of point estimates will be calculated using the normal approximation for quantitative data and the exact binomial distribution (Clopper-Pearson method) for proportions.

#### 5.1.3.1 Safety Analysis

The safety analysis will report the occurrence of solicited reactions and the incidence of unsolicited AEs between Visit 1 and Visit 2 (or between Visit 1 and Visit 3 for those subjects receiving 2 doses).

To avoid any under-estimation of the incidences, the number of subjects with documented safety will be used as denominator for the frequencies.

- For solicited reactions, the denominator will be the total number of subjects who have non-missing data for the endpoint considered
- For unsolicited AEs, the denominator will be the total number of subjects who were vaccinated at the dose analyzed

The safety tables will be produced using a subject approach; i.e., number of subjects who experienced at least 1 safety event during a considered period.

The 2-sided 95% CIs for the percentages will be calculated using the exact binomial method (Clopper-Pearson method).

#### *Solicited reactions*

The solicited injection site reactions and the solicited systemic reactions will be presented separately (except in summary tables).

Solicited reactions will be presented according to their nature (MedDRA [the latest version at database lock] PT), intensity (Grade 1, 2, or 3), time to onset, and number of days of occurrence.

#### *Unsolicited AEs*

Unsolicited AEs included in the analysis will be summarized in the safety overview and analyzed according to their nature (MedDRA [the latest version at database lock] system organ class [SOC] and PT classification) and relationship to the vaccination.

#### *Injection Site Reactions*

For each treatment group, the number and percentage of subjects experiencing any injection site reaction after injection will be calculated.

The description of injection site reactions will be presented according to:

- Solicited injection site reactions
  - All solicited injection site reactions that occur each day within 7 days after injection will be analyzed.
- Unsolicited injection site reactions

All unsolicited injection site reactions between Visit 1 and Visit 2 (or between Visit 1 and Visit 3 for those subjects receiving 2 doses) will be described according to the type of events.

### ***Systemic Events and Reactions***

For each treatment group, the number and percentage of subjects experiencing any unsolicited immediate systemic event in the 20 minutes after injection will be calculated.

In addition, the description of systemic events will be structured according to:

- **Solicited systemic reactions**

All solicited systemic reactions that occur each day within 7 days after injection will be analyzed.

- **Unsolicited systemic events**

All unsolicited systemic events between Visit 1 and Visit 2 (or between Visit 1 and Visit 3 for those subjects receiving 2 doses) will be described according to the type of events.

### ***Serious Adverse Events***

The number and percentage of subjects with SAEs after vaccination between Visit 1 and Visit 2 (or between Visit 1 and Visit 3 for those subjects receiving 2 doses) in each treatment group will be calculated by outcome, seriousness, and relationship to vaccination.

#### **5.1.3.2 Immunogenicity Analysis**

All analyses will be descriptive; no hypotheses will be tested. The following immunogenicity parametersa will be calculated for each influenza strain with 95% CIs:

- Geometric mean HAI assay titers at pre-vaccination and post-final vaccination
- Geometric means of the individual titer ratios of post-final vaccination/pre-vaccination
- Seroprotection rates: The percentages of subjects with a titer  $\geq 40$  (1/dil) at pre-vaccination and at post-final vaccination
- Seroconversion rates: The percentages of subjects with either a pre-vaccination titer  $< 10$  (1/dil) and a post-final vaccination titer  $\geq 40$  (1/dil), or a pre-vaccination titer  $\geq 10$  (1/dil) and a  $\geq 4$ -fold increase in post-final vaccination titer

## **5.2 Analysis Sets**

Three analysis sets will be used: the Safety Analysis Set, the Full Analysis Set (FAS), and the Per-Protocol Analysis Set (PPAS).

---

a Post-final vaccination in each of the immunogenicity parameters is defined as 28 (window, 28–35) days post-final vaccination for subjects 6 months to  $< 9$  years of age, and 21 (window, 21–28) days post-vaccination for subjects  $\geq 18$  years of age

### 5.2.1 Safety Analysis Set

The Safety Analysis Set is defined as those subjects who have received at least 1 dose of the study vaccine.a Subjects 6 months to < 9 years of age will have their safety analyzed after “any dose” according to the study vaccine they received as the first dose. Safety analysis after each dose will be assessed in the subset of the Safety Analysis Set having received that dose. All subjects will have their safety data analyzed after each vaccination according to the vaccine they actually received for that dose. Safety data recorded for a vaccine other than the assigned study vaccine will be excluded from the study statistical summaries and listed separately.

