Statistical Methods:	
Summaries of the recruitment and baseline demographic characteristics of the study subjects will be presented. The number of subjects enrolled and their age at enrollment (mean, median, and minimum and maximum), sex, race, and ethnic origin will be summarized, along with the number and description of protocol violations.
 
For the main safety and immunogenicity parameters, 95% confidence intervals (CIs) of point estimates of proportions will be calculated using the normal approximation for quantitative data and the exact binomial distribution (Clopper-Pearson method) for proportions. All analyses will be descriptive; no hypotheses will be tested.
 
Safety
 
The Safety Analysis Set will be used for the safety analyses. Subjects will be analyzed according to the vaccine they actually received.
 
Immunogenicity
 
The immunogenicity analyses will be performed on both the Full Analysis Set and the Per-Protocol Analysis Set. Data will be summarized and presented for each age group.

	
The following immunogenicity parameters^a will be calculated for each influenza strain with 95% CIs:
 
• Geometric mean HAI assay titers at pre-vaccination and post-final vaccination• Geometric means of titer ratios (post-final vaccination divided by pre-vaccination).• Seroprotection rates: The percentages of subjects with a titer ≥ 40 (1/dil) at pre-vaccination and at post-final vaccination• Seroconversion rates: The percentages of subjects with either a pre-vaccination titer < 10 (1/dil) and a post-final vaccination titer ≥ 40 (1/dil), or a pre-vaccination titer ≥ 10 (1/dil) and a ≥ 4-fold increase in post-final vaccination titer 
^a Post-final vaccination in each of the immunogenicity parameters is defined as 28 (window, 28–35) days post-final vaccination for subjects 6 months to < 9 years of age, and 21 (window, 21–28) days post-vaccination for subjects ≥ 18 years of age.

--	--

Tables of Study Procedures

Study Flow Chart for Subjects 6 Months to < 9 Years of Age: 2 or 3 Visits, 1 or 2 Vaccinations

Visit Number	All Subjects		Subjects Receiving 1 Dose of Influenza Vaccine	Subjects Receiving 2 Doses of Influenza Vaccine		
	Visit 1	Telephone Contact		Visit 2	Telephone Contact	Visit 3
Study Timelines	Day 0	Visit 1 + 8 days	Visit 1 + 28 days	Visit 1 + 28 days	Visit 2 + 8 days	Visit 2 + 28 days

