5.2.7.2 Definitive Contraindications

Should a subject experience 1 or more of the conditions listed below, after the first dose of study vaccine, the Investigator will not administer the second dose of vaccine that has been allocated for use in the study (i.e., study vaccine); however, the Investigator may administer a second dose of licensed, non-study influenza vaccine in accordance with standard clinical care.

Definitive contraindications include but are not limited to:

- An anaphylactic or other significant allergic reaction to the previous dose of vaccine.
- Receipt of any non-study vaccine (including a non-study dose of 2017–2018 influenza vaccine), immune globulins, blood, or blood-derived products between Visit 1 and Visit 2.
- Bleeding disorder, receipt of anticoagulants, or thrombocytopenia, which may be a contraindication for intramuscular vaccination, at the discretion of the Investigator.
- Development of any condition that in the opinion of the Investigator would pose a health risk to the subject or could interfere with the evaluation of the study vaccine (including GBS, clinically significant developmental delay, neurologic disorder, seizure disorder, human immunodeficiency virus infection, hepatitis B, or hepatitis C).
- Development of an immunodeficiency; or receipt of immunosuppressive therapy such as anti-cancer chemotherapy or radiation therapy; or receipt of long-term systemic corticosteroid therapy (prednisone or equivalent for more than 2 consecutive weeks).
- Adverse events that are considered a contraindication for further participation in the study.

Subjects with a definitive contraindication will continue to be followed for the study-defined safety and immunogenicity assessments, as applicable. Therefore, in this study subjects with a definitive contraindication will be discontinued from the study; but, will continue to be followed for study-defined safety assessments. For safety follow-up of subjects who experience definitive contraindications, see Section 5.2.11.

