6.6 Treatment Compliance

The following measures will ensure that the vaccine doses administered comply with those planned, and that any non-compliance is documented so that it can be accounted for in the data analyses:

- All vaccinations will be administered by qualified study personnel
- The person in charge of product management at the site will maintain accountability records of product delivery to the study site, product inventory at the site, dose(s) given to each subject, and the disposal of unused or wasted doses

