12.3 Handling of Missing Data and Outliers

12.3.1 Safety

No imputation of missing data will be conducted. All subjects with safety data and all safety data recorded in the eCRFs will be included in the safety analyses. No search for outliers will be performed.

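### Read literally, the exclusion sentence in the Safety Analysis Set cancels the as-received rule for a Quadrivalent/High-Dose swap and leaves those events, including any SAE, only in a listing (minor)

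*SAP*

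**What the plan says.** SAP 5.2.1 sets three rules in a row.

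- Per dose: "All subjects will have their safety data analyzed after each vaccination according to the vaccine they actually received for that dose".
- Any-dose table: children 6 months to < 9 years are analyzed "according to the study vaccine they received as the first dose". Protocol 12.2.1 applies this to all subjects.
- Exclusion: "Safety data recorded for a vaccine other than the assigned study vaccine will be excluded from the study statistical summaries and listed separately".

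Protocol 12.2.1 has the per-dose rule in almost the same words and repeats the exclusion sentence.

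Four other places bear on the point.

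- Protocol synopsis, Statistical Methods: "Subjects will be analyzed according to the vaccine they actually received". No exclusion is mentioned.
- Protocol 12.3.1: "All subjects with safety data and all safety data recorded in the eCRFs will be included in the safety analyses".
- Protocol 5.2.7.2, on children with a definitive contraindication to the second study dose: "the Investigator may administer a second dose of licensed, non-study influenza vaccine in accordance with standard clinical care". Safety follow-up continues for these children.
- SAP 5.1.3.1: "For unsolicited AEs, the denominator will be the total number of subjects who were vaccinated at the dose analyzed". The stated aim of the denominator rules is to avoid under-estimating incidence.

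**The concern.** The per-dose rule and the exclusion sentence give opposite instructions for the same event. If a subject assigned Quadrivalent is given High-Dose by mistake, or the reverse, the first sentence summarizes the events under the vaccine received. The second sends them to a listing. Neither document says which prevails, and neither exempts SAEs.

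A serious event after a swapped dose could therefore be missing from the SAE summary in SAP 5.1.3.1. Adverse events of special interest are captured as SAEs (SAP 4.3.1.2), so they would be missing with it. If the event leaves the numerator while the subject stays in the denominator, the rate is biased downward, against the stated aim of SAP 5.1.3.1. Two programmers reading the text in good faith could produce different tables. That choice is better fixed before the data are seen.

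**Working it through.** **Which doses are affected.** Both documents use the term assigned at subject level, with one study vaccine per age group (protocol 5.1.3 and 6.5; SAP 3.2). That leaves four situations.

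| Vaccine given | As-received sentence | Exclusion, literal | Exclusion limited to non-study vaccines |
|---|---|---|---|
| The assigned study vaccine | Summarized | No effect | No effect |
| The other study vaccine (swap) | Summarized by vaccine received | Listing only | Summarized by vaccine received |
| Non-study influenza vaccine as second dose | No study column fits | Listing only | Listing only |
| Wrong volume of Quadrivalent | Summarized, column not stated | Unclear | Summarized, column to be stated |

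The two readings clearly differ only in the swap row. There the literal reading leaves the as-received sentence nothing to do, and it contradicts the synopsis and protocol 12.3.1. The narrower reading makes all four texts agree.

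The wrong-volume row is unclear because the 0.25-mL and 0.5-mL syringes are both Licensed Product 1 (protocol 6.1.1). SAP 5.2.1 speaks of a vaccine, while the per-protocol rule in SAP 5.2.3 speaks of a vaccine dose.

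**Size.** The plan states no figure on this point to reproduce. Its group sizes add up: 4 × 60 = 240. Intervals below are two-sided 95% Clopper-Pearson, the method in SAP 5.1.3.1. For x events in n subjects, the lower limit is the 2.5% quantile of Beta(x, n − x + 1) and the upper limit is the 97.5% quantile of Beta(x + 1, n − x). For x = 0 the lower limit is 0 and the upper limit is 1 − 0.025^(1/n).

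*Any-dose table.* Assume a group of 60 children. One has a correct first dose, a swapped second dose, and an event only after the second dose. The first-dose rule keeps the child in the group.

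- Only event in the group, counted: 1/60 = 1.67% (0.04 to 8.94).
- Same event excluded, child kept in the denominator: 0/60 = 0% (0 to 5.96).
- Same event excluded, child also removed: 0/59 = 0% (0 to 6.06).
- Common reaction, counted: 30/60 = 50.00% (36.81 to 63.19).
- Common reaction, excluded: 29/60 = 48.33% (35.23 to 61.61).

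With the denominator held at 60, each affected child moves the rate by 1/60 = 1.67 points.

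*Dose-2 unsolicited-AE table.* The number of two-dose children is not given. Assume 15, 30 or 60, with counted events in 20% of them and the swapped child's own event excluded. Keeping or removing that child in the denominator gives:

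- 3/15 = 20.00% or 3/14 = 21.43%
- 6/30 = 20.00% or 6/29 = 20.69%
- 12/60 = 20.00% or 12/59 = 20.34%

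The difference is 0.3 to 1.4 points.

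*Where nothing changes.* In a per-dose table, if the swapped subject leaves both numerator and denominator of the assigned group, that group's rate is the same under either reading. The only difference is whether the events appear in a summary by vaccine received or in a listing.

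**The case against.** The strongest reply is that the text can be read consistently. The Safety Analysis Set is defined by receipt of study vaccine, with a footnote restricting it to vaccine for which safety data are scheduled to be collected. If the exclusion covers only non-study vaccines, nothing conflicts, and protocol 5.2.7.2 supplies the case it was written for. The literal reading also makes the preceding sentence almost pointless, which argues against it as the intent. This stands as the probable intent. It does not settle the wording: the protocol uses the term non-study in 5.2.7.2 and 6.7 but not here, and the phrase it does use covers the other study vaccine as well.

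A second reply is that groups are defined by age and product together, so a swapped subject fits no planned column and a transparent listing is a fair display. This largely stands. A separate row with one subject is close to a listing.

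Third, the trigger is rare. The IRT provides the vaccine and dose and staff confirm it (protocol 6.5). Both pediatric groups receive Quadrivalent, and the second dose is confirmed again through the IRT (protocol 5.1.4). This stands too.

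Fourth, two supporting texts are weaker than they look. The protocol 12.3.1 sentence is a general one in the missing-data section, and SAP 5.3.1 does not repeat it. Protocol 6.6 says that "any non-compliance is documented so that it can be accounted for in the data analyses", and a listing is one way to do that.

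A reader might go further and infer that the plan sets out to drop SAEs, or that serious events could be lost. The documents do not support this. Every SAE must be reported to the sponsor within 24 hours whatever its cause (protocol 10.1), the safety and clinical databases are reconciled (protocol 11.2), and excluded data are still listed. A reader might also infer that a wrong volume of Quadrivalent triggers the exclusion. The text leaves that open.

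**Conclusion.** The conflict is real but minor. Followed as written, the sentence takes events after a Quadrivalent/High-Dose swap, SAEs included, out of the statistical summaries, contrary to the as-received rule beside it, the synopsis and protocol 12.3.1. It may also leave numerator and denominator mismatched for unsolicited AEs.

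The effect is zero if no dosing error occurs, and the documents give no error rate. If one occurs, it is about 1.7 percentage points per affected subject in a group of 60. The denominator question alone is worth 0.3 to 1.4 points under the assumed numbers of two-dose children and the assumed 20% event rate. The study is descriptive and tests no hypothesis, so no inference turns on this. What is at stake is whether a rare event, above all an SAE, appears in the summary tables or only in a listing.

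**What to change.** In SAP 5.2.1 and protocol 12.2.1:

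1. Replace the description of the excluded vaccine with *a non-study vaccine*.
2. Add that SAEs after any study vaccine stay in the SAE summary, by vaccine received.
3. State that the same subjects form numerator and denominator in every safety table, and align the unsolicited-AE denominator in SAP 5.1.3.1 with this.

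The any-dose rule can stay: a child remains in the first-dose group with all events after study vaccine, and a footnote identifies any swapped second dose.

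Two smaller clarifications can go in with these: how a subject who fits no planned age and product group is displayed (a separate row or a footnoted listing), and whether a wrong volume of Quadrivalent counts as another vaccine for the analysis.

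The cost is one or two sentences in each document before database lock, minor programming, and possibly one extra table row. No new data are needed.

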### 5.2.2 Full Analysis Set

The FAS is defined as those subjects who have received at least 1 dose of the study vaccine and have a valid post-final vaccination serology result for at least 1 strain.

### 5.2.3 Per-Protocol Analysis Set

The PPAS is a subset of the FAS. The subjects presenting with at least 1 of the following relevant protocol deviations will be excluded from the PPAS:

- Subject did not meet all protocol-specified inclusion criteria or met at least 1 of the protocol specified exclusion criteria
- Subject did not complete the vaccination schedule including a partially administered vaccination/dose
- Subject did not complete the second dose of study vaccine with a definitive contraindications as defined in the protocol after the first dose
- Subject received a vaccine dose other than the one that he/she was assigned to receive, or was assigned by mistake to another age group
- Preparation and/or administration of vaccine was not done as per-protocol
- Subject did not provide a post-dose serology sample in the proper time
- Subject received a protocol-prohibited therapy/medication/vaccine that might impact antibody response to the study vaccine
- Any other deviation identified during conduct of the study and judged by the clinical team during data review as having a potential impact on the assessment of immunogenicity

